### 5.6.4 Immunoglobulins at screening

Blood samples will be collected for evaluation of the following by ImmunoCAP:

- Total IgE [ku/L]
- Grass specific IgE [ku/L]
- Grass specific IgG4 [mg/L]

These classes will be summarized by display of the absolute and relative frequencies per class by treatment group for the FAS and the SAF.

## 5.7 Efficacy

### 5.7.1 Primary efficacy variable: Average CSMS over the peak GPS

The primary efficacy variable is the daily Combined Symptom and Medication Score (CSMS) averaged over the peak Grass Pollen Season (GPS).

#### 5.7.1.1. Definition of the Grass Pollen Season

For the purpose of statistical analysis, the start and end of the entire grass pollen seasons

(GPS) and the peak pollen seasons of each year (if applicable) will be determined based on the daily pollen counts from pollen traps local to the trial sites.

The final decisions regarding the site-specific (peak) pollen periods to be applied for the eDiary related endpoints will be determined prior to unblinding of the database and documented in the BDRM minutes for each year.

#### 5.7.1.2. Daily Combined Symptom and Medication Score (CSMS)

The daily CSMS is the sum of the daily Symptom Score (dSS) component of the CSMS (CSMS-dSS) and the daily Medication Score (dMS) component of the CSMS (CSMS-dMS) calculated from the data recorded in the eDiary.

The CSMS-dSS is calculated as the sum of the severity of conjunctival symptoms (2 items) and nasal symptoms (4 items) divided by 6 for each subject and day (see Table 2).

The severity of symptoms is recorded on a 4-point severity scale

- 0 = No symptoms,
- 1 = Mild symptoms,
- 2 = Moderate symptoms, and
- 3 = Severe symptoms.

**Table 2: Conjunctival and nasal symptoms of the CSMS**

Conjunctival Symptoms	Itchy/red eyes *
	Watery eyes
Nasal Symptoms	Blocked nose
	Runny nose
	Itchy nose
	Sneezing

\* Maximum of single items "Itchy eyes" and "Red eyes" is used for analysis.

The CSMS-dMS is equal to the raw score assigned to each subject and day for the medication with the highest step taken that day.

Thereby, medication is rated on a 4-point scale

- 0 = No relief medication used,
- 1 = Oral antihistamine/Ocular antihistamine (Step 1 medication),
- 2 = Intranasal corticosteroids (Step 2 medication) with Step 1 medication(s), and
- 3 = Oral corticosteroids (Step 3 medication) with Step 1 and Step 2 medications.

Hence, the CSMS-dSS and the CSMS-dMS each range from 0 to 3 and the daily CSMS thus ranges from 0 to 6.

#### 5.7.1.3. Average CSMS over the peak GPS

The average CSMS of the peak GPS is calculated as the sum of the daily CSMS within the peak GPS divided by the number of days of the peak GPS where the CSMS has been collected.

Subjects with missing average CSMS over the peak GPS will be included in the primary analysis by using multiple imputation methods on a by-subject level.

Summary statistics will be provided for the average CSMS over the peak GPS by treatment group based on observed cases.

#### **5.7.1.4. Primary efficacy analysis**

The primary efficacy endpoint will be evaluated using a linear mixed model and non-parametric approaches.

The mixed model is accounting for the heterogeneity across countries and will include:

- Average CSMS over the peak GPS as outcome variable.
- Treatment group as main fixed effect
- Country as a random factor.

The difference between PQ Grass and placebo treatment groups will be estimated using least square (LS) means along with the corresponding 2-sided 80% confidence intervals (CIs) of the difference of LS means.

The difference in CSMS will also be presented as a relative percentage change with respect to the LS mean in the corresponding placebo group, and the CI will be calculated by approximating the standard error using the delta method.

The primary analysis specified above will be performed for all imputed datasets and the resulting least square (LS) means are averages over the analyses performed on the single imputed datasets. The difference on the relative scale will be calculated based on the combined LS means.

For linear mixed models, parameter estimation and inference is based on the assumption that the residuals are normally distributed and the random affects are normally distributed and uncorrelated. To verify the validity of the results, several plots are generated based on observed cases only:

- Scatter plots of marginal residuals against their predicted values.
- Histogram of marginal residuals.
- Q-Q plot of marginal residuals.

As a non-parametric approach the Wilcoxon Rank Sum test will be performed for pairwise comparisons without accounting for any potential covariates and country heterogeneity.

The primary efficacy analysis will be performed on the FAS.

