Allergy Therapeutics (UK) Ltd.: PQGrass309 Study Protocol

Status:

final

Clinical Trial Title:

A randomised, double-blind, placebo-controlled exploratory study to explore the efficacy and safety of PQ Grass 27600 SU in subjects with seasonal allergic rhinitis and/or rhinoconjunctivitis induced by grass pollen exposure

NCT04687059

Investigational Product:

PQ Grass

Clinical Phase:

Phase II/III

Sponsor:

Allergy Therapeutics (UK) Ltd.
[name]
[name]
Worthing
United Kingdom

Date:

August 3, 2021

Protocol Title: A randomised, double-blind, placebo-controlled exploratory study to explore the efficacy and safety of PQ Grass 27600 SU in subjects with seasonal allergic rhinitis and/or rhinoconjunctivitis induced by grass pollen exposure.

Short Title: *An exploratory study of PQ Grass 27600 SU.*

Phase: Phase II/III

Sponsor: Allergy Therapeutics (UK) Ltd, [name].

Study centres: The study is expected to be conducted in the European Union (EU) (Germany and/or Poland) and the United States of America (US) and include approximately 15 study sites in total (7 centres in the EU and 8 centres in the US).

Rationale:

The PQGrass309 (G309) clinical trial is the exploratory Phase II/III field study with PQ Grass. The aim of the G309 pivotal clinical trial is to explore the efficacy and safety of the optimal effective dose of PQ Grass 27600 SU using 2 pre-seasonal treatment regimens ~ (conventional and extended). The efficacy will be assessed through the measurements of the effect of PQ Grass on the symptoms of seasonal allergic rhinitis (SAR)/rhinoconjunctivitis and the use of relief medications to control these symptoms during the peak grass pollen season (GPS).

Number of subjects planned: The study will enrol enough subjects to allow treatment of approximately 150 subjects.

Study period: Estimated first subject enrolled (Q3/2020) and last subject last visit (Q3/2021). The end of study (EoS) is defined as the date of the last 6 months telephone follow-up call of the last subject in the study.

Objectives and endpoints:

Objectives	Endpoints
Primary	
To explore the efficacy of PQ Grass 27600 SU in grass pollen induced seasonal allergic rhinitis and/or rhinoconjunctivitis in a field setting.	The CSMS averaged over the peak grass pollen season (GPS).
Secondary	
Efficacy	

Objectives	Endpoints

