Abbreviations: AE = adverse events; AESI = adverse events of special interest; CPT = conjunctival provocation test; CSMS = combined symptom and medication score; dMS = daily medication score; dSS = daily symptom score; GPS = grass pollen season; Ig = immunoglobulin; PEFr = peak expiratory flow rate; RQLQ(S) = rhinoconjunctivitis quality of life questionnaire with standardised activities; SU = standardised units; TCS = total combined score; TSS = total symptom score.	

Overall design:

This will be a multi-centre, randomised, parallel group, double-blind, placebo-controlled exploratory study to explore the efficacy and safety of PQ Grass. Subjects will be assigned in a ratio of 2:2:1:1 (PQ Grass conventional posology, PQ Grass extended posology, placebo containing MCT and placebo without MCT, respectively) to receive one of the following treatment options prior to the onset of the grass pollen season (GPS):

- **PQ Grass conventional posology:** 4 injections of placebo without MCT followed by 6 injections of PQ Grass (900, 2700, 6000, 6000, 6000 and 6000 SU sequentially), to achieve a cumulative dose of 27600 SU *or*
- **PQ Grass extended posology:** 4 injections initially of PQ Grass (900, 2700, 6000, 6000 SU sequentially) followed by 1 injection of placebo without MCT, followed by 1 injection of PQ Grass (6000 SU), followed by 3 injections of placebo without MCT and thereafter 1 injection of PQ Grass (6000 SU) to achieve a cumulative dose of 27600 SU *or*
- **Placebo containing MCT:** 4 injections of placebo without MCT followed by 6 injections of placebo containing MCT *or*
- **Placebo without MCT:** 10 injections of placebo without MCT.

The study includes 4 periods, encompassing 15 visits to the study site and at least 2 follow-up telephone calls. Subjects will be provided with enough relief medication to cover them through this period by the study site. Eligible subjects will be randomised to either PQ Grass (conventional posology), PQ Grass (extended posology), placebo containing MCT or placebo without MCT treatment groups and will receive the first injection at the study. Subjects will thereafter return to the study site at subsequent visits during the treatment period (Visit 3 to Visit 11) to receive the remaining injections. The average duration of the treatment period will be approximately 16 weeks.

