This is an exploratory field study which will aim to randomise 150 subjects, with approximately 50, 50, 25 and 25 subjects randomised to PQ Grass 27600 SU (conventional posology), PQ Grass 27600 SU (extended posology), placebo containing MCT and placebo without MCT, respectively. This number is considered adequate for an exploratory study to verify the assumptions for the coefficient of variation (CV) of the placebo and the average reduction in CSMS after treatment with PQ Grass compared to placebo (both expressed as percentages and as absolute differences) during the peak GPS. The findings from this exploratory study will support the sample size calculations of a subsequent pivotal Phase III study for PQ Grass (PQGrass306).

The primary endpoint of the study will be the CSMS averaged over the peak GPS.

The difference in CSMS between PQ Grass (conventional posology) and placebo (i.e., the placebo containing MCT group and the placebo without MCT group) and the difference between PQ Grass (extended posology) and the placebo groups will be evaluated using parametric (i.e., linear mixed effects model) / non-parametric models as appropriate. The 2 placebo groups will both be combined and analysed as separate groups if there is <5% effect-size difference and similar variability between the 2 groups. Otherwise, they will only be analysed as independent groups.

Secondary efficacy endpoints derived from the CSMS, TCS, daily symptom score (dSS) and daily medication score (dMS) (for both the CSMS and TCS) and for the peak/entire (or truncated) GPS, immunological responses, probability of well days and quality of life will be evaluated using comparable linear mixed effects model and sensitivity analyses as in the primary efficacy analysis.

The frequency, relationship and severity of AEs and frequency of premature discontinuations from treatment or study due to AEs will be assessed within each treatment group. Changes in vital signs, clinical laboratory parameters and peak expiratory flow rate (PEFR) in subjects with past or current asthma will be analysed using descriptive statistics and 2-sided 95% confidence intervals (CIs) within each treatment group. All other safety data will be analysed descriptively.

Trial Oversight Committee: Yes.

Adjudication Committee: Yes.

Schedule of activities

	Period 1 Screening	Period 2 Randomisation and Treatment					Period 3 Pre/during/end of GPS Assessments				Period 4	

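### Country, with two or three levels, is the only random factor and site is not modelled: the treatment difference stays valid, but precision is lost and the placebo LS mean's standard error is unreliable

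*SAP*

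**What the plan says.** The protocol synopsis (Study centres) states: "The study is expected to be conducted in the European Union (EU) (Germany and/or Poland) and the United States of America (US"). Country therefore has two or three levels. The same entry plans "approximately 15 study sites in total (7 centres in the EU and 8 centres in the US").

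SAP 5.7.1.1 says the season limits are "determined based on the daily pollen counts from pollen traps local to the trial sites", and that the site-specific periods are settled before unblinding.

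SAP 5.7.1.4 fits treatment group as the fixed effect and "Country as a random factor". No site, region or pollen term appears. It reports LS-mean differences with two-sided 80% intervals, and the same difference as a percentage of the placebo LS mean with a delta-method interval. The rank test is run "without accounting for any potential covariates and country heterogeneity". No degrees-of-freedom method is named.

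SAP 5.7.2.1 to 5.7.2.3 repeat this analysis for the other season averages. SAP 5.7.2.6 and 5.7.2.7 use the same structure with a baseline covariate.

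The protocol's statistical section says the sample size is adequate to "verify the assumptions for the coefficient of variation (CV) of the placebo and the average reduction in CSMS" after treatment, as percentages and as absolute differences, in support of the sample size of PQGrass306.

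**The concern.** A variance component estimated from two or three groups is barely estimable. It nevertheless enters the standard error of each LS mean, and through the placebo LS mean it enters the interval for the percentage reduction.

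Meanwhile the level at which pollen exposure is measured, the site, is left out. Site-specific windows align the outcome in time, but differences between sites in the level of exposure and symptoms stay in the residual.

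The non-parametric analysis drops the one adjustment that the model makes. It also gives a test without an estimate or interval, in a study that reports estimates with 80% intervals. Because the trial is meant to inform the size of a later study, precision and reproducibility are a large part of what it delivers.

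**Working it through.** **Inputs from the documents.** 150 subjects; "Subjects will be assigned in a ratio of 2:2:1:1"; two or three countries; about 15 sites; 80% intervals. The split reproduces: 150 × 2/6 = 50 and 150 × 1/6 = 25, giving 50/50/25/25. No power, SD or effect size is stated, so everything below that needs a variance is an assumption.

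**1. Country variance.** With k groups, the 95% limits for the between-group SD are the estimate times √[(k−1)/χ²(0.975)] and √[(k−1)/χ²(0.025)].

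| Grouping | df | Multipliers on the SD |
|---|---|---|
| 2 countries | 1 | 0.45 to 31.9 |
| 3 countries | 2 | 0.52 to 6.3 |
| 15 sites | 14 | 0.73 to 1.58 |

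**2. Chance of a zero estimate.** For the ANOVA estimator this is P(F < 1/(1 + n₀τ²/σ²)), where τ is the country SD and σ the residual SD. With two countries of 75, n₀ = 75. With 40/35/75, n₀ = (150 − 8450/150)/2 = 46.8. At CV 60%, a country SD of 12% of the placebo mean is 0.2σ, and 20 to 30% is 0.33σ to 0.5σ.

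| Country SD, % of placebo mean | 2 countries | 3 countries |
|---|---|---|
| 12 | 38% | about 30% |
| 20 | 26% | 15% |
| 30 | 18% | 8% |

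**3. Simulation.** 1500 runs per scenario; 15 sites of 10; 50 conventional, 50 extended, 50 pooled placebo; residual SD 1.0, placebo mean 1.5, true difference −0.3 (also 0). All these values except the site count and arm sizes are assumed.

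*Placebo LS mean.* With country and site SD both 0.3 to 0.5, the nominal 80% interval on about 143 df covered 64 to 68% (two countries) or 70 to 73% (three). Part of this shortfall comes from the unmodelled site variation. The 80% t multiplier is 1.29 on 143 df, 1.89 on 2 and 3.08 on 1, so the unstated df method matters a great deal for this interval.

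*Treatment difference.* Bias was at most about 0.01 and coverage 0.78 to 0.81 under random country. Mean 80% half-widths:

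| Country SD / site SD (2 countries) | Random country | Fixed country | Random site |
|---|---|---|---|
| 0 / 0 | 0.256 | 0.257 | 0.256 |
| 0.3 / 0.3 | 0.267 | 0.268 | 0.263 |
| 0.5 / 0.5 | 0.284 | 0.284 | 0.266 |

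Fixing country alone therefore does almost nothing for the difference. The gain comes from the site term: 0.267/0.263 = 1.015 at a site ICC of 0.09/1.09 = 8%, and 0.284/0.266 = 1.068 at 0.25/1.25 = 20%.

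**4. Site left in the residual.** Without site-stratified randomisation, the country-only SE of the difference exceeds the SE with fixed country and random site by 0.7%, 2.3% and 6.8% at ICC 5%, 10% and 20%. Across the checks run the range was about 1 to 8%. If arms were balanced within every site, the bound 1 − √(1 − ICC) applies: 1 − √0.95 = 2.5% and 1 − √0.80 = 10.6%.

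**5. Relative effect.** Let R = μT/μP − 1, in units of the placebo mean, with 50 per group, equal SDs and equally weighted countries. The sampling variance is (CV²/50)(1 + (1+R)²). The random country term adds (τ²/k)R². With CV = 0.60:

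- R = −0.20: sampling part 0.0072 × 1.64 = 0.01181.
- R = −0.30: sampling part 0.0072 × 1.49 = 0.01073.

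| R | τ | Added, k = 2 | SE increase | Added, k = 3 | SE increase |
|---|---|---|---|---|---|
| −0.20 | 0.12 | 0.00029 | 1.2% | 0.00019 | 0.8% |
| −0.20 | 0.30 | 0.00180 | 7.4% | 0.00120 | 5.0% |
| −0.30 | 0.12 | 0.00065 | 3.0% | 0.00043 | 2.0% |
| −0.30 | 0.30 | 0.00405 | 17.4% | 0.00270 | 11.9% |

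The largest increases go with the lower chances of a zero estimate in step 2, so the two extremes do not occur together.

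**6. Rank test.** With no true effect, the Wilcoxon test rejected in 20.5% of runs at the 20% level, so its level holds. With a true difference and both SDs 0.5 (two countries) it rejected in 48.6%, against 52.8% for the planned model and 56.1% with random site. In a separate check, stratifying the rank test gave power 0.57 against 0.51 to 0.56 unstratified.

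**The case against.** The strongest reply is that the main estimate is sound. Treatment is randomised, and additive country effects largely cancel in the difference. A reader might infer from a poorly estimated random factor that the treatment effect is biased or its error rate inflated. Neither the documents nor the simulations support that: null rejection at the 20% level was 0.21 for the mixed model. This part of the reply stands in full.

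Second, calling the relative-effect interval too wide presumes that the target is the countries studied. If the sponsor wants inference to a wider population of countries, including country variance is legitimate. In simulation the planned relative interval kept about 80% coverage for such a population, whereas the fixed-country interval covered that value only 70 to 80% of the time. This stands as a choice to be declared, though two or three selected countries are a weak basis for the wider claim.

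Third, a reader might infer that the input to PQGrass306 is compromised. The protocol names the placebo CV and the reduction, not an interval, and the placebo mean and SD can be taken from the observed-case summaries in SAP 5.1.1 and 5.7.1.3.

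Fourth, the SAP openly discloses that the Wilcoxon test is unadjusted, and the test is valid. SAP 2.1 also defers further exploratory and sensitivity analyses to a separate plan, which might include site. That would leave the primary model as it is.

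Finally, about 10 subjects per site at 2:2:1:1 is under two per placebo arm per site (10/6 = 1.7), so a site term needs a rule for sparse sites.

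**Conclusion.** The concern holds as a matter of precision and reproducibility. The absolute difference is unbiased with about nominal coverage. What suffers is:

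- the country variance, on 1 or 2 df, and with it the standard error of the placebo LS mean;
- the relative-effect SE, larger by about 1 to 17% with two countries or 1 to 12% with three, relative to inference for the studied countries;
- the absolute-difference interval, wider by about 1 to 8% for want of a site term (2.5 to 11% only if arms are balanced within sites).

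These sizes rest on assumed values: CV 60%, country SD 12 to 30% of the placebo mean, a true reduction of 20 to 30%, and site ICC 5 to 20%. The documents give none of them, and the available text does not state the randomisation strata. The country count is the planned one. The change is worth making because it is cheap, not because the planned analysis is invalid.

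**What to change.** In SAP 5.7.1.4:

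- Fit country as a fixed effect and site, or pollen-trap region, as the random effect. Pool sparse sites by a rule set before unblinding.
- Name the degrees-of-freedom method.
- State that the relative effect then refers to the countries studied.
- Replace the unstratified Wilcoxon test with a van Elteren test stratified by country, and add a Hodges-Lehmann shift with an 80% interval.
- Carry the same terms into the repeated secondary models, and check that the multiple-imputation model is consistent with them.

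The cost is 1 or 2 degrees of freedom out of about 145, the sparse-site rule, SAP wording and programming, and inference limited to the studied countries. No additional data are needed.

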### 5.7.2.2. Average CSMS-dSS and CSMS-dMS over the peak and the entire (truncated) GPS

The average CSMS-dSS over the peak and the entire (truncated) GPS and the average CSMS-dMS over the peak and the entire (truncated) GPS is calculated in the same way as the average CSMS over the peak GPS.

The primary efficacy analysis will be repeated for

- the averaged CSMS-dSS over the peak GPS for the FAS,
- the averaged CSMS-dMS over the peak GPS for the FAS,
- the averaged CSMS-dSS over the entire (truncated) GPS for the FAS, and
- the averaged CSMS-dMS over the entire (truncated) GPS for the FAS.

Summary statistics will be provided for all average scores by treatment group.

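### The delta-method CI for the percentage change in CSMS has unequal tails that favour overstating the reduction, and it can disagree with the absolute-difference CI from the same model.

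*SAP*

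**What the plan says.** SAP 5.7.1.4 fits a linear mixed model to the average CSMS over the peak season, with treatment fixed and country random. It reports differences of LS means with the "corresponding 2-sided 80% confidence intervals (CIs) of the difference of LS means". It then adds a second scale: "The difference in CSMS will also be presented as a relative percentage change with respect to the LS mean in the corresponding placebo group", and for that scale "the CI will be calculated by approximating the standard error using the delta method". After multiple imputation, the relative difference is computed from the combined LS means. The SAP does not give the scale on which the interval is built, say whether the covariance of the LS means enters, or restate the confidence level for the percentage.

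The primary analysis is repeated for one score in SAP 5.7.2.1, four in 5.7.2.2 (for example "the averaged CSMS-dMS over the peak GPS for the FAS") and six in 5.7.2.3.2, so 1 + 4 + 6 = 11 further scores.

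The protocol synopsis (Statistical methods) plans "approximately 50, 50, 25 and 25 subjects randomised to PQ Grass 27600 SU (conventional posology" and the remaining arms in order. Its pooling rule reads "The 2 placebo groups will both be combined and analysed as separate groups if there is <5% effect-size difference and similar variability"; if the condition fails, the placebo groups are analysed only separately. A single placebo group of about 25 is therefore a denominator in every case. The synopsis also says that the study should verify the placebo CV and the average CSMS reduction, "both expressed as percentages and as absolute differences", to support the sample size of a later pivotal study.

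**The concern.** A ratio with an imprecise denominator has a skewed sampling distribution. When the placebo mean is high by chance, the apparent reduction is larger and the delta-method standard error is smaller, because the placebo mean divides both. A symmetric interval around the ratio is then too short on the side of no effect and too long on the other. The limit nearest no effect, which a cautious reader would look at, is the optimistic one.

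The SAP also puts two intervals for the same contrast side by side. If they can disagree on whether no effect is compatible with the data, the report needs a rule for which one to believe, and the SAP has none.

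**Working it through.** **Inputs from the documents.** The protocol allocates 2:2:1:1 among 150 subjects: 150 × 2/6 = 50 and 150 × 1/6 = 25, which reproduces the planned arm sizes. The level is 80% two-sided, so 10% per tail and z = 1.2816. It is stated for the absolute difference and assumed here for the percentage too. The documents give no coverage figure to reproduce.

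**Assumptions.** The documents give no CV, SD or expected reduction. CVs of 0.5 to 1.0 and a true reduction of 20% are used below, with wider ranges where stated.

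**Formulas.** Let A and P be the active and placebo LS means, R = A/P, and vA and vP their variances in units of P². Ignoring the country variance:
- absolute difference in placebo means: (R − 1) ± z·√(vA + vP)
- delta, ratio scale: (R − 1) ± z·√(vA + R²·vP)
- log-ratio delta: R·exp(±z·√(vA/R² + vP)) − 1
- Fieller: [R ± z·√(vA + R²·vP − g·vA)]/(1 − g) − 1, with g = z²·vP

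Whenever R is below 1, R²·vP is smaller than vP. The percentage interval is then narrower than the absolute one, and both are centred at R − 1. Fieller limits include R = 1 exactly when the absolute interval includes zero, given the same variances and quantile.

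**Worked example: observed reduction 20%, CV 0.7, 50 vs 25.** vA = 0.49/50 = 0.0098; vP = 0.49/25 = 0.0196.
- Absolute: √0.0294 = 0.1715; −0.2 ± 0.2197 gives **−0.42 to +0.02** (includes no effect)
- Delta: √(0.0098 + 0.64 × 0.0196) = √0.02234 = 0.1495; −0.2 ± 0.1916 gives **−39.2% to −0.8%** (excludes no effect)
- Fieller: g = 1.6424 × 0.0196 = 0.0322; (0.8 ± 0.1902)/0.9678 − 1 gives **−37.0% to +2.3%** (includes no effect)

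The same formulas at CV 0.6 and observed reduction 20%:

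| Placebo n | Delta | Log-ratio | Fieller |
|---|---|---|---|
| 25 | −36.4% to −3.6% | −34.8% to −1.8% | −34.8% to −1.3% |
| 50 | −33.9% to −6.1% | −32.8% to −4.8% | −33.1% to −5.0% |

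**Tail rates by simulation.** Gamma outcomes, true ratio 0.8, equal SDs, arms of 50/50/25/25, common residual variance on 146 df. Entries are the delta interval's misses; coverage is 100 minus their sum.

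| Placebo n | CV | Overstating side | Other side | Coverage |
|---|---|---|---|---|
| 25 | 0.5 | 12.1% | 7.1% | 80.8% |
| 25 | 0.7 | 12.9% | 5.9% | 81.2% |
| 25 | 1.0 | 13.7% | 3.1% | 83.2% |
| 50 | 0.7 | 11.7% | 7.7% | 80.6% |

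In the n = 25 scenarios, Fieller limits miss about 10.3-10.5% on the overstating side and 9.4-9.9% on the other. The log-ratio interval at CV 0.7, n = 25 gives 10.3% and 8.9%.

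**Sensitivity.** Normal, gamma and bounded 0-6 outcomes were tried with CV 0.4 to 1.0, reductions of 0-30%, and SDs equal or proportional to the mean. A simplified run added a country effect with SD up to 0.2 of the placebo mean. The overstating-side miss at n = 25 was 10.9-14.8% and the other side 2.4-10.1%. At n = 50 with equal SDs the overstating-side miss was 9.9-12.8%. With SD proportional to the mean and a 30% reduction it was 9.0-10.5%, so there the excess nearly or fully goes. Multiple imputation was not modelled.

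**The case against.** The case for leaving the plan alone has several parts.

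- **Coverage.** A reader might infer that the interval excludes the truth more than 20% of the time. With equal SDs it does not: total coverage was 80.0-83.8%. Coverage fell to 77.6-80.6% with SD proportional to the mean and reductions of 20-30%, but Fieller fell too (77.0-77.8%), so that loss comes from the common variance. This stands: the defect is where the misses fall.
- **Scale.** The SAP does not say that the interval is untransformed. A delta-method standard error for the log ratio, back-transformed, also fits its sentence. This stands, and if the log scale was meant, saying so largely settles the point.
- **Size.** At n = 25 and CV 0.5-0.7 the excess is 2 to 3 points over a 10% tail, and with pooled placebo it is about 1 to 2. At CV 1.4 and n = 25 the split reaches 14.7%/0.4%, but applying that CV to the medication score is conjecture. This stands.
- **Use.** A reader might infer that the pivotal sample size will be biased. The documents do not say that a confidence limit feeds that calculation, and neither the point estimate nor the placebo CV depends on the interval method. This stands.
- **Fieller's own limits.** At CV 1.4 and n = 25 the placebo mean is typically 5/1.4 = 3.6 standard errors from zero, but single trials can be far lower. The limits become unbounded below about 1.3. A fallback is therefore needed.

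None of this answers the unequal tails on the natural reading, or the possible conflict between the two intervals.

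**Conclusion.** The concern holds in a limited form. Read naturally, SAP 5.7.1.4 gives the percentage change a symmetric ratio-scale interval. With about 25 placebo subjects, equal SDs, CVs of 0.5-1.0 and a true reduction of 20%, it errs wholly towards overstatement in about 12-14% of trials and the other way in about 3-7%, against 10% each. With pooled placebo the imbalance is smaller and in some settings vanishes. When a reduction is observed, the interval can exclude no effect while the absolute CI includes it.

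The documents support neither a claim of deficient overall coverage nor a claim that any trial decision turns on this interval: the study is exploratory and has no success rule tied to it. The point is still worth acting on, because the percentage reduction is a named output of the study and its reported limits would change.

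**What to change.** In SAP 5.7.1.4, compute the CI for the percentage change at the stated 80% level by Fieller's method, from the combined LS means and their combined covariance matrix over the imputed datasets. If the Fieller limits are unbounded, use the back-transformed delta-method CI for log(PQ Grass/placebo). Using that log-ratio interval throughout is an acceptable simpler choice, though only Fieller limits agree exactly with the absolute CI about no effect. Apply the same rule to the 11 repeated analyses in SAP 5.7.2.1, 5.7.2.2 and 5.7.2.3.2. If a log scale was already intended, state it.

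The cost is one SAP sentence and a few lines of code; no new data are needed and no point estimate changes. The interval becomes asymmetric and its limit nearest no effect slightly less favourable, for example −1.3% instead of −3.6% at an observed reduction of 20%, CV 0.6 and 25 placebo subjects.
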